#### **8.1.2.3 Sensitivity Analyses for the Primary Endpoint**

In addition to presenting the primary efficacy endpoints with HCV RNA and SVR12 and SVR24 imputed as described in Section 8.1, SVR12 and SVR24 will be presented using the following other methods to impute missing post-treatment virologic results:

- Imputing any missing HCV RNA values in the SVR12/SVR24 window by carrying forward the last non-missing (post-baseline) HCV RNA value prior to the SVR12/SVR24 window;
- Imputing as described in Section 8.1 but exclude the subjects who were categorized as "prematurely discontinued study drug with no on-treatment virologic failure" and "missing follow-up data in the PT Period."

For each of these, the simple percentage of subjects with SVR12/SVR24 will be presented along with a 2-sided 95% CI using Wilson score method.

As a sensitivity analysis, comparisons of the SVR12 and SVR24 rates may be made to geographic region-specific SVR rates with IFN based therapy (IFN [alpha, beta or pegIFN] with RBV) treatment.

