## **8.0 Statistical Methods and Determination of Sample Size**

### **8.1 Statistical and Analytical Plans**

An interim analysis will occur after all enrolled subjects from S. Korea and Taiwan have completed the Treatment Period through Post-Treatment Week 12 of the Post-Treatment Period or prematurely discontinued from the study. This interim analysis is planned to support regulatory submission activities in S. Korea and Taiwan. The primary analysis will occur after all subjects have completed PT Week 24 or prematurely discontinued the study. All remaining data through PT Week 48 will be summarized in the end of study analysis.

SAS® (SAS Institute, Inc., Cary, NC) for the UNIX operating system will be used for all analyses. All confidence intervals will be 2-sided with an  $\alpha$  level of 0.05. Descriptive statistics will be provided, such as the number of observations (N), mean, and standard deviation (SD) for continuous variables and counts and percentages for discrete variables.

Efficacy, safety, and demographic analyses will be performed on the intent-to-treat (ITT) population which will consist of all enrolled subjects who receive at least one dose of study drug. Additional summaries will be provided by geographic region (China, S. Korea, Taiwan).

No data will be imputed for any efficacy or safety analyses except for the PRO questionnaires and for analyses of the HCV RNA endpoints of RVR, EOTR, and all SVR endpoints. If a respondent answers at least 50% of the items in a multi-item scale of the SF-36v2, the missing items will be imputed with the average score of the answered items in the same scale. In cases where the respondent did not answer at least 50% of the items, the score for that domain will be considered missing. The Mental and Physical Component Summary measures will not be computed if any domain is missing. If a respondent answers at least 12 of the 16 items on the HCVPRO, the missing items will be imputed with the mean score of the answered items. In cases where the respondent did not answer five or more items, the HCVPRO total score will be considered missing. For EQ-5D-5L index and VAS scores, no imputation will be performed for missing items.

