HCV RNA values will be selected for the analyses of HCV RNA endpoints of RVR, EOTR, and all SVR endpoints based on the defined visit windows. When there is no HCV RNA value in a visit window based on defined visit windows, the closest values before and after the window, regardless of the value chosen for the subsequent and preceding window, will be used for the flanking imputation described below.

If a subject has a missing HCV RNA value at a post-baseline visit but with undetectable or unquantifiable HCV RNA levels at both the preceding value and succeeding value, the HCV RNA level will be considered undetectable or unquantifiable, respectively, at this visit for this subject. Subsequent to this flanking imputation, if a subject is missing a value for the visit window associated with the analysis, the subject will be imputed as a visit failure (i.e., not undetectable or unquantifiable). For SVR analyses (e.g., SVR4, SVR12, SVR24) if after performing the flanking imputation there is no value in the appropriate window but there is an HCV RNA value after the window, then it will be imputed into the SVR window.

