### **8.1.2.1 Primary Efficacy Endpoints**

For South Korea and Taiwan the primary endpoint is:

- A1. SVR12: Superiority to the historical SVR rate for telaprevir plus pegIFN/RBV therapy; the LCB of the 95% CI for the percentage of subjects with SVR12 must exceed 67% to achieve superiority.

For China, the primary endpoints are:

- B1. SVR12: Superiority to the historical SVR rate for telaprevir plus pegIFN/RBV therapy; the LCB of the 95% CI for the percentage of subjects with SVR12 must exceed 67% to achieve superiority.
- B2. SVR24: Superiority to the historical SVR rate for telaprevir plus pegIFN/RBV therapy; the LCB of the 95% CI for the percentage of subjects with SVR24 must exceed 67% to achieve superiority.

For China, in order to control the Type I error rate at 0.05, a fixed-sequence testing procedure will be used to proceed through the primary efficacy endpoints. That is, only if success has been demonstrated for the primary endpoint of superiority of SVR12 rate to the historical rate for telaprevir plus pegIFN and RBV therapy (B1) will the testing continue to the second primary endpoint of superiority of the SVR24 rate to the historical rate for telaprevir plus pegIFN and RBV therapy (B2).

To test the hypothesis that the percentage of treatment-naïve and IFN based therapy (IFN [alpha, beta or pegIFN] with RBV) treatment-experienced HCV genotype 1b infected Asian subjects with compensated cirrhosis treated with ABT-450/r/ABT-267 + ABT-333 + RBV for 12 weeks who achieve SVR12 is superior to a clinically meaningful threshold

based on the historical SVR rates for the HCV genotype 1 infected population treated with telaprevir plus pegIFN/RBV, the percentage of subjects with SVR12 will be calculated with a 2-sided 95% CI using Wilson score method, and the LCB will be compared to the defined threshold. The LCB of the 95% CI of SVR12 must be greater than 67% in order for the regimen to be considered superior.

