## **8.2 Determination of Sample Size**

It is planned to enroll approximately 100 subjects (60 from China, 20 from South Korea and 20 from Taiwan). All subjects will receive ABT-450/r/ABT-267 + ABT-333 coadministered with RBV for 12 weeks. With a total sample size of about 100 subjects and assuming that 94% of the subjects will achieve  $SVR_{12}$ , this study has greater than

90% power to demonstrate SVR12 superiority with a 2-sided 95% lower confidence bound greater than 67% (based on the normal approximation of a single binomial proportion in a one-sample test for superiority using EAST 6.2). The SVR24 rate is anticipated to be very similar to the SVR12 rate and thus the power should still be at least 90%. No adjustment for dropout is applicable because subjects who do not have data at Post-Treatment Week 12 (after imputing) are counted as failures for SVR12 and SVR24.

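### The carry-forward sensitivity analysis lets an on-treatment HCV RNA value count as SVR12 or SVR24, and no planned analysis removes the favourable imputation steps while keeping missing as failure

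*Protocol*

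**What the plan says.** **Definition.** Section 5.3.3.1 defines SVR12 and SVR24 as HCV RNA below LLOQ 12 and 24 weeks after the last actual dose of study drug.

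**Primary rule (Section 8.1).**
- A missing visit counts as suppressed if the values on both sides of it are suppressed (flanking).
- For the SVR endpoints, if the window is still empty but "there is an HCV RNA value after the window, then it will be imputed into the SVR window".
- A subject still without a value is a failure. Section 8.2 repeats this as the reason for making no dropout adjustment.

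**Sensitivity analyses (Section 8.1.2.3).**
- Carry-forward: an empty window is filled "by carrying forward the last non-missing (post-baseline) HCV RNA value prior to the" window.
- Exclusion: "Imputing as described in Section 8.1 but exclude the subjects who were categorized as" early stoppers without on-treatment virologic failure or as lacking post-treatment follow-up data.
- A third, optional comparison changes the reference rate and does not concern missing data.

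**Decision rule (Section 8.1.2.1).** The SVR percentage "will be calculated with a 2-sided 95% CI using Wilson score method, and the LCB will be compared to the defined threshold". That bound "must be greater than 67% in order for the regimen to be considered superior".

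**The concern.** The only limit on the carried value is that it be post-baseline, so values taken on drug qualify. Section 5.4.1.1 stops study drug in subjects who do not reach HCV RNA below LLOQ by Week 6 and in those with confirmed rebound. Most later on-treatment values will therefore be below LLOQ. A subject who leaves at Week 8 and never returns is then an SVR12 and an SVR24 success, although nothing was measured after treatment. Relapse happens after treatment by definition, so this imputation cannot detect it.

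The exclusion analysis appears to take failures out of the denominator, so it also tends to sit above the primary. Meanwhile the two steps in the primary that can turn a missing window into a success are never switched off in an analysis that keeps missing as failure. At stake is how informative the supportive analyses are. The success decision itself does not depend on them.

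**Working it through.** **Inputs.** Section 8.2 plans about 100 subjects, "assuming that 94% of the subjects will achieve" SVR12. The threshold is 67%. The interval is two-sided 95% Wilson, z = 1.96. The numbers of missing and imputed subjects below are assumptions, because the protocol projects none.

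**1. The plan's own figure.** Power by the normal approximation:

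Φ{[(0.94 − 0.67) − 1.96·√(0.67·0.33/100)] / √(0.94·0.06/100)} = Φ{(0.27 − 0.0922)/0.0237} = Φ(7.5), which is above 99.99%.

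The exact calculation at the Wilson cut-off of 77/100 also exceeds 99.99%. The stated power of greater than 90% is correct.

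**2. Direction of carry-forward against the primary.** The cases are a missing window with a value before it:

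| Value before window | Value after window | Primary | Carry-forward | Change |
|---|---|---|---|---|
| < LLOQ | < LLOQ | success | success | none |
| < LLOQ | ≥ LLOQ | failure | success | up |
| < LLOQ | none | failure | success | up |
| ≥ LLOQ | < LLOQ | success | failure | down |
| ≥ LLOQ | ≥ LLOQ | failure | failure | none |
| ≥ LLOQ | none | failure | failure | none |

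The usual case, suppressed and then lost, is the third row. The downward row needs a value at or above LLOQ before the window and a suppressed one after it. That could be an unconfirmed blip, or a relapser later suppressed on other treatment, and should be rare.

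**3. Size.** Wilson lower bound, with p = x/n:

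L = [p + z²/2n − z·√(p(1−p)/n + z²/4n²)] / (1 + z²/n)

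Worked for 76/100: (0.7792 − 1.96·0.0438)/1.0384 = 0.668.

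In the table, m is the assumed number of subjects who were suppressed at last contact, were then lost, and are failures in the primary.

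| Primary | m | Carry-forward | Exclusion |
|---|---|---|---|
| 94/100, L 87.5% | 2 | 96/100, L 90.2% | 94/98, L 90.0% |
| 94/100, L 87.5% | 6 | 100/100, L 96.3% | 94/94, L 96.1% |
| 76/100, L 66.8% | 2 | 78/100, L 68.9% | 76/98, L 68.3% |

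In the last row the primary fails and both supportive analyses exceed 67%.

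For the scale of m, Section 3.0 gives 91.8% SVR12 among 208 subjects in the 12-week arm of Study M13-099. That is about 191 successes and 17 non-responders, of whom 13 were virologic failures. The remaining 4 are 4/208 = 1.9%, so m = 2 per 100 is more realistic than m = 6.

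**4. What a strict analysis could change.** Start from 94/100 and turn j successes that rest on flanking or later values into failures:

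| j | Successes | Lower bound |
|---|---|---|
| 0 | 94 | 87.5% |
| 1 | 93 | 86.3% |
| 3 | 91 | 83.8% |
| 5 | 89 | 81.4% |
| 10 | 84 | 75.6% |
| 17 | 77 | 67.8% |
| 18 | 76 | 66.8% |

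The result is lost only at j = 18.

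**5. By region.** Section 8.1.2.1 lists endpoints by region, while Section 8.2 sizes only the total. If the endpoints are read by region:
- South Korea and Taiwan (n = 40) need 33 successes. A result of 38/40 is lost after 6 reversals.
- China (n = 60) needs 48. A result of 56/60 is lost after 9.

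**The case against.** A reader might infer that the plan has no conservative analysis and that its primary is therefore biased upward. The documents do not support this. For subjects with no usable value the primary is already the worst case, since no method can score them below failure. Alternatives that sit above it are a consequence of that choice. The shifts in step 3 come entirely from subjects whom the primary already counts as failures, so they give no support for a strict table. That case rests on step 4 alone.

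A reader might also infer that no planned analysis can fall below the primary. Carry-forward can, as the fourth row of the direction table shows. The direction of the exclusion analysis depends on two categories that the protocol does not define. It is upward if they are reasons for not reaching SVR, but not necessarily if they include early stoppers who did reach it.

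The other side has further good points:
- Flanking needs observed suppression on both sides, and a later value at or above LLOQ is imputed as failure.
- Post-treatment HCV RNA is drawn at Weeks 2, 4 and 8 (Table 6), so the carried value will often be post-treatment.
- Relapse is a secondary endpoint in its own right (Section 8.1.2.2).
- In the 12-week arm of Study M13-099, 12 of 13 virologic failures were relapses, but that arm mixed genotypes 1a and 1b. Table 1 shows 100% SVR12 for genotype 1b cirrhotics on this regimen, except 6/7 in prior partial responders. The relapse share should not be transferred to this trial.
- An extra supportive table is often left to the SAP, which is not shown.

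All of this limits the importance of the point. It does not answer the wording defect: the carry-forward rule is stated in the protocol and, as written, admits a value that cannot measure the endpoint.

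**Conclusion.** The point holds and is minor. Carry-forward is flawed as written because an on-treatment value can stand in for SVR12 or SVR24, against the definition in Section 5.3.3.1. This follows from the text alone and needs no assumption about numbers. The two sensitivity analyses are generally, though not always, more lenient than the primary, by about 2 percentage points for every 2 subjects per 100 who are suppressed and then lost. Flanking and later-value imputation are not removed in any analysis that keeps missing as failure.

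The trial's conclusion is not in doubt on this account. Success rests on the primary alone, and at the planned 94% with 100 subjects about 18 imputed successes would have to reverse. The margin would be smaller if the endpoints are judged by region.

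**What to change.** In Section 8.1.2.3:

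(a) Restrict carry-forward to HCV RNA values obtained after the last dose of study drug, and count subjects with no such value as failures. The analysis will still tend to be lenient, but it will rest on post-treatment evidence.

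(b) Add one supportive table each for SVR12 and SVR24 that uses only values observed inside the SVR window, with missing as failure and no flanking or later-value imputation. If the SAP already holds this table, a cross-reference is enough.

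The cost is a change of wording and one table per endpoint from data already collected. The supportive figures may come out slightly lower. The primary analysis, its threshold and the sample size do not change.

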#### 8.1.2.4 Subgroup Analysis

The percentage (with 2-sided 95% confidence intervals) of subjects with SVR12 and SVR24 will be presented for the following subgroups:

- Treatment-naïve versus previous IFN based therapy (IFN [alpha, beta or pegIFN] with RBV) treatment-experienced subjects;
  - For treatment-experienced subjects, type of response to previous IFN based therapy (non-responder, relapser, or (IFN based therapy intolerant);
  - For non-responders to previous IFN based therapy, type of response (null responder, partial responder, or other non-responder);
  - Geographic region/previous HCV treatment status (China/treatment-naïve, China/treatment-experienced, S. Korea/treatment-naïve, S. Korea/treatment-experienced, Taiwan/treatment-naïve, Taiwan/treatment-experienced).
- IL28B genotype (CC or non-CC), (CC, CT, or TT);
- Baseline HCV RNA level (< 800,000 IU/mL or ≥ 800,000 IU/mL);
- Baseline IP-10 (< 600 pg/mL or ≥ 600 pg/mL);
- Baseline HOMA-IR (< 3 or ≥ 3 mU × mmol/L);
- Sex (male versus female);
- Age (< 55 versus ≥ 55 years), (< 65 versus ≥ 65 years);
- BMI (< 30 or ≥ 30 kg/m^2);
- Subjects with RBV dose modifications (yes/no);
- Presence of hepatic steatosis at Baseline (yes/no);
- Hepatoprotective drug use at baseline (yes/no);
- History of Diabetes (yes/no);
- History of Bleeding Disorders (yes/no);
- History of Depression or Bipolar Disorder (yes/no);
- Former injection drug user (yes/no);
- Baseline Child-Pugh Score ( 5, 6, or > 6);
- Baseline platelets (< 90 or ≥ 90 × 10^9cells/L);

- Baseline albumin ( $< 35$  or  $\geq 35$  g/L);
- Baseline alpha fetoprotein [AFP] ( $< 20$  or  $\geq 20$  ng/mL).

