## **6.7 Toxicity Management**

For the purpose of medical management, all adverse events and laboratory abnormalities that occur during the study must be evaluated by the Investigator. A table of Clinical Toxicity Grades for evaluating laboratory abnormalities is provided in [Appendix C](#). This table should be used in determination of the appropriate toxicity management as discussed in Section [6.7.1](#) and Section [6.7.5](#).

A drug-related toxicity is an adverse event or laboratory value outside of the reference range that is judged by the Investigator or the Sponsor as having a "reasonable possibility" of being related to the study drug (Section [6.3](#)). A toxicity is deemed "clinically significant" based on the medical judgment of the Investigator. Laboratory abnormalities will be managed as deemed clinically appropriate by the investigator until resolved.

Investigators should avoid interrupting study drugs for more than 7 consecutive days. The Investigator should ensure that any study drug interruptions or RBV dose modifications and associated adverse events are promptly entered into the appropriate eCRFs.

The toxicity management guidelines below should be followed throughout the Treatment Period of the study.

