### **6.7.3 Management of Hemoglobin Decreases**

Reductions in hemoglobin are a well characterized side effect of ribavirin exposure. If a subject experiences a hemoglobin decrease meeting one of the criteria outlined in [Table 13](#), a confirmatory test should be performed. If the hemoglobin decrease is confirmed, the management guidelines in [Table 13](#) should be followed. Management will be different for subjects without a history of known cardiac disease and subjects with known cardiac disease.

Use of hematologic growth factors (such as erythropoietin or filgrastim) or blood transfusions are permitted at the discretion of the Investigator. Management of hematologic growth factor therapy is the responsibility of the Investigator, and growth factors will not be provided by AbbVie.

Alternate management of hemoglobin decreases outside of these criteria requires approval of the AbbVie Study Designated Physician.

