### 6.7.5 Management of eGFR Decreases

If calculated eGFR is confirmed to have decreased to  $< 50$  mL/minute, medical evaluation should include a full review of current medications, including those taken on an as needed basis, those which are sold over the counter and any dietary and herbal supplements, and appropriate dose reduction or discontinuation based on impaired renal function should be done (if applicable). Ribavirin dose should be adjusted as in [Table 15](#). Alternative management of RBV dose in the setting of reduced renal function will require approval of the AbbVie Study Designated Physician.

The investigator should also consider whether drug-drug interactions with concomitant medications may have contributed to the decrease in eGFR, and whether discontinuation of substitution of the possible interacting drug should be considered. For example, drug interactions between DAAs and some antihypertensive medications could potentially increase exposures of the antihypertensive and may reduce renal function. If anti-hypertensive medications are adjusted, vital signs must be monitored to ensure appropriate blood pressure control. Refer to Section 5.2.3.3 for additional information regarding drug-drug interactions.

If eGFR improves, the site should perform all necessary readjustment of any dose modifications that have been made.

The Investigator should ensure that any concomitant medication changes, RBV dose reductions, and study drug discontinuations, as well as consequent related adverse events are entered into the appropriate eCRFs.

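### SVR by ribavirin dose modification (yes/no) is a post-baseline split that probably favours the modified group by construction; present it at a landmark instead

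*Protocol*

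**What the plan says.** Protocol Section 8.1.2.4 (Subgroup Analysis) asks for "The percentage (with 2-sided 95% confidence intervals) of subjects with SVR"12 and SVR24 across one undivided list. The list covers treatment history, region, IL28B genotype, baseline laboratory values, demographics and medical history, and also "Subjects with RBV dose modifications (yes/no". It sets no time window, minimum exposure or caveat for that item. Section 8.1.1 does not list it as a baseline characteristic.

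Other sections show when a modification can arise:

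- Section 6.7: "The toxicity management guidelines below should be followed throughout the Treatment Period of the study".
- Section 6.7.3, for hemoglobin: "If the hemoglobin decrease is confirmed", the Table 13 guidelines apply.
- Section 6.7.5, for a confirmed fall in eGFR: "Ribavirin dose should be adjusted as in" Table 15.

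Section 8.1.2 places all efficacy analyses in the intention-to-treat population. On data still absent once neighbouring values have been used to fill gaps, Section 8.1 has this rule: "if a subject is missing a value for the visit window associated with the analysis, the subject will be imputed as a visit failure". For SVR, a later HCV RNA value can still fill an empty window. Section 8.2 relies on the same rule: "No adjustment for dropout is applicable because subjects who do not have data at Post-Treatment Week 12 (after imputing) are counted as failures".

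**The concern.** The Yes group is defined by an event that takes time to occur. A subject who leaves in the first weeks has had little opportunity for a modification and will usually be classed No. This is the structure of immortal-time bias, and two routes feed it.

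- **Early loss.** A subject lost early with no later HCV RNA value is scored a failure, usually in No.
- **Early virologic failure.** Section 5.4.1.1 requires subjects who meet the virologic failure criteria to stop study drug. Their time at risk of a modification is cut short, and no missing data are needed.

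Both routes move failures into No for reasons unrelated to ribavirin dose. Few failures are expected, so one or two subjects can settle which group looks better. A reader of the table could conclude that modifying ribavirin costs no efficacy in cirrhotic patients, when the layout alone would produce that impression.

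**Working it through.** **The plan's own figure.** The protocol gives no figure for this subgroup. The nearest is the power statement in Section 8.2: above 90% for about 100 subjects, 94% against 67%. The normal approximation gives (0.94 − 0.67 − 1.96 × √(0.67 × 0.33/100)) / √(0.94 × 0.06/100) = (0.27 − 0.0922)/0.0237 ≈ 7.5, so power exceeds 99.9%. The statement holds, and nothing below changes it.

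**Set-up for the illustration (assumed, apart from N and the 94%).**

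- N = 100 with 94 responders and 6 failures, from Section 8.2.
- d subjects are lost before any modification, are scored as failures, and fall in No.
- Among the other 100 − d, a fraction m is modified, and modification is unrelated to SVR.

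Among those remaining, SVR is s = 94/(100 − d). This is also the Yes rate. The No group has n(No) subjects, of whom d are certain failures, so its rate is s × (1 − d/n(No)). Hence

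gap (Yes − No) = s × d / n(No).

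Example with d = 2 and m = 10%: s = 94/98 = 0.959; Yes = 0.10 × 98 ≈ 10; No = 90; gap = 0.959 × 2/90 = 2.1 points.

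| d lost early | s | gap, m = 10% | gap, m = 20% | gap, m = 30% |
|---|---|---|---|---|
| 1 | 94/99 = 0.949 | 1.1 (No = 90) | 1.2 (No = 80) | 1.4 (No = 70) |
| 2 | 94/98 = 0.959 | 2.1 (No = 90) | 2.4 (No = 80) | 2.7 (No = 71) |
| 4 | 94/96 = 0.979 | 4.4 (No = 90) | 4.8 (No = 81) | 5.5 (No = 71) |
| 6 | 94/94 = 1.000 | 6.6 (No = 91) | 7.4 (No = 81) | 8.3 (No = 72) |

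The true effect of modification is zero in every cell. The last row is the extreme in which all six failures are early losses.

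**Are the inputs plausible?** Table 3 reports hemoglobin below 10 g/dL in 7.2% of the 12-week cirrhotic arm of Study M13-099. With m = 7% and d = 2, the gap is 0.959 × 2/93 = 2.1 points. SVR12 in that arm was 91.8% of 208, about 191 responders and 17 failures. Thirteen failures were virologic, leaving about 4 of 208 (1.9%), or roughly 2 per 100. That arm mixed genotypes 1a and 1b. In Table 1 the only genotype 1b shortfall on the 12-week regimen is one partial responder (6/7), so d could be below 2 here.

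**With a landmark.** If the d subjects are lost before the landmark they leave the table, and both groups have rate s. The gap from this mechanism is then 0.

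**The case against.** Several points on the other side stand.

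- **Early stopping is not failure.** Subjects who stop early are followed for 48 weeks (Section 5.1.3). SVR is counted from the last actual dose (Section 5.3.3.1), and a later HCV RNA value can fill an empty SVR window (Section 8.1). A reader might infer that every early stopper becomes a failure in No. The protocol supports this only for those lost without later data and for virologic failures.
- **The direction is not certain.** A subject who stops for anemia may already have had ribavirin reduced or interrupted, and would then be Yes. The protocol does not say whether interruption or discontinuation of ribavirin counts as a modification.
- **The table is descriptive.** Percentages and intervals are planned, with no test or stated difference between groups. The intervals are wide: 19 of 20 in Yes gives a Wilson interval of 76.4% to 99.1%, against an artefact of about 2.4 points.
- **Nothing is mislabelled.** The section is headed only as subgroup analysis and never calls the list baseline.
- **It is not the only look at ribavirin.** A reader might infer that it is. Ribavirin concentrations are collected and summarised, and Section 8.1.6 plans exposure-response work, including logistic regression on SVR12 and relapse.

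It can also be said that timing rules belong in the statistical analysis plan, which is not at hand. That answers less. The protocol already fixes an undated yes/no split, the intention-to-treat population and missing as failure, and carrying those out as written produces the problem.

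**Conclusion.** The point holds in limited form. Ribavirin modification is a post-baseline classifier placed among pre-treatment factors, and under the planned population and missing-data rule the table probably favours Yes by construction. About 2 early-lost subjects in 100 would give a spurious gap of roughly 2 to 3 points, and one would give about 1.

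These sizes assume 94% SVR overall, that all early-lost subjects fall in No, 10% to 30% of the remainder modified, and no true effect of modification. They describe a mechanism and do not forecast the result.

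A reader might go further and infer that the trial's efficacy conclusion is at risk. It is not: the primary endpoints, their error control and the sample size do not use this split. The change is worth making because it is cheap and the table invites a causal reading.

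**What to change.** Take the item out of the general list in Section 8.1.2.4 and present it separately as a post-baseline exposure summary:

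1. Name a fixed landmark visit in advance. Include only subjects still on study drug at that visit, and classify them by whether ribavirin was modified up to then.
2. State whether interruption or discontinuation of ribavirin counts as a modification, and how a subject whose ribavirin is interrupted while the other study drugs continue is handled.
3. Label the table as post-baseline and not for causal reading.

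Do not restrict the table to study drug duration of at least 77 days, the completion definition in Section 8.1.2.5. That would condition on finishing treatment. It would remove on-treatment virologic failures who stopped before that point, and subjects who stopped for toxicity after a ribavirin reduction, which are outcomes the table should be able to show.

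The cost is a wording change, with no new data or subjects. Subjects who stopped before the landmark drop out of this one table, and modifications after it count as No. A later landmark captures more modifications but leaves out more subjects.
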